1.6. Risks/Benefits of Investigational Product and Safety Population

The safety and tolerability profiles of the apremilast 20 mg BID and 30 mg BID dose groups are both acceptable based on results from the clinical development program for apremilast. Treatment-emergent adverse events (TEAEs) associated with apremilast treatment were diarrhea, nausea, headache (including tension headache), and upper respiratory tract infection, which were usually mild or moderate in severity and often resolved while subjects continued to take apremilast. Diarrhea, nausea and headache tended to occur early in treatment. The overall discontinuation rate due to AEs was low and was most frequently due to nausea, diarrhea, or headache. Treatment with apremilast was associated with observed weight loss without overt clinical consequences. The results of pivotal Phase 3 clinical trials in psoriasis and PsA demonstrate that the 30 mg BID dose presents a favorable benefit/risk profile in adult subjects

with moderate to severe psoriasis and PsA. All apremilast approvals to date for both PsA and psoriasis have been for the 30 mg BID dose regimen.

Please refer to the IB for detailed information concerning the available pharmacology, toxicology, drug metabolism, clinical studies, and the safety profile of apremilast.

CELGENE PROPRIETARY INFORMATION

2. STUDY OBJECTIVES

2.1. Primary Objective

The primary objective of the study is to select a pediatric dose of apremilast based on the safety, tolerability, and PK of apremilast in adolescents and children with moderate to severe plaque psoriasis.

2.2. Secondary Objectives

The secondary objective is to evaluate the taste and acceptability of apremilast tablet using a faces Likert Scale.

2.3. Exploratory Objectives

The exploratory objective of the study is to evaluate the effect of apremilast on psoriasis in adolescents and children as measured by PASI.

3. STUDY ENDPOINTS

3.1. Primary Endpoint(s)

Safety

The safety (reported AEs) and laboratory findings of subjects in each age group will be described and evaluated in relation to the extent of exposure to apremilast.

The following will be monitored, evaluated, recorded, and reported:

- Adverse events (AEs)
- Physical examinations
- Vital sign measurements
- Clinical laboratory safety tests
- 12-lead electrocardiograms (ECGs)
- Concomitant medications / procedures
- Pregnancy tests

Pharmacokinetics

The following PK parameters will be estimated for apremilast using a non-compartmental approach if data permit:

- Maximum observed plasma concentration (C_{max})
- Time to C_{max} (t_{max})
- Area under the plasma concentration-time curve from time zero to 12 hours postdose (AUC_{0-12})
- Area under the plasma concentration-time curve from time zero to the last quantifiable concentration (AUC_{0-t})
- Apparent total plasma clearance when dosed orally (CL/F)
- Apparent total volume of distribution when dosed orally, based on steady-state (V_{ss}/F) or the terminal phase (V_z/F)
- Terminal-phase elimination half-life ($t_{1/2}$)

The following population PK parameters will be determined as appropriate:

- CL/F
- Apparent total volume of distribution when dosed orally (V/F)
- Absorption rate constant (first-order; K_a)
- Lag (if applicable)

3.2. Secondary Endpoint(s)

The taste and acceptability of apremilast tablet will be assessed using a faces Likert Scale on Day 1, initial dosing.

3.3. Exploratory Endpoint(s)

The exploratory endpoint is the percent change in PASI scores from Baseline.

Measurements of PASI will be performed at Screening, Baseline, Weeks 2, 4, 8, 16, 24, 32, 40, 50, 54, 58, Unscheduled visits, and Early Termination visits as indicated in the Table of Events (Section 5).

4. OVERALL STUDY DESIGN

4.1. Study Design

This is a Phase 2, multicenter, open-label study in subjects with moderate to severe plaque psoriasis aged 6 to 17 years, inclusive, intended to assess the safety, tolerability, and PK of apremilast with 2 weeks of oral apremilast treatment followed by a 48-week extension of apremilast treatment. Moderate to severe plaque psoriasis is defined as Psoriasis Area Severity Index (PASI) ≥ 12 , Body Surface Area (BSA) $\geq 10\%$, and static Physician Global Assessment (sPGA) of ≥ 3 (moderate to severe) [See [Appendix A](#)]. The total study duration for each subject will last for up to a total of 107 weeks which includes screening, treatment (including the PK portion of the study and the extension treatment period), two short-term follow-up periods and a long-term follow-up period ([Figure 1](#)).

Each subject will undergo a screening period of up to 5 weeks, a treatment period of 2 weeks with PK sample collection, and an extension treatment period of 48 weeks, to allow subjects access to apremilast treatment if medically appropriate (following the completion of the 2 week PK portion). Regardless of when they stop treatment, subjects should complete two post treatment follow-up visits at approximately 4 and 8 weeks after the last dose.

All subjects should complete the final follow-up visit at Week 102 or at a timepoint 52 weeks after the last dose of apremilast was taken in subjects who have withdrawn at any time prior to Week 50.

At least 32 subjects will be enrolled into this study to provide an adequate PK profile and safety assessment in subjects of different ages and body weight ranges. Subjects will be divided into 2 age groups (adolescents [ages 12 to 17 years, inclusive] and children [ages 6 to 11 years, inclusive]), with at least 16 subjects in each group. Apremilast treatment will start in older and heavier subjects.

A staggered, stepwise approach by age range and weight (starting with older and heavier subjects) is considered appropriate for this first-time-in-children study. Doses for younger and lower body weight subjects will be adjusted based on safety and PK data from older and heavier subjects. Dosing within and between groups will be staggered as described below, and in [Figure 2](#), based on PK data collected and a minimum of 2 weeks of safety data.

Group 1 (ages 12 to 17 years, inclusive; weight ≥ 35 kg)

- At least 8 subjects will initially be enrolled into Group 1 and will weigh ≥ 35 kg.
 - Dosing for subjects with a weight ≥ 35 kg to < 70 kg will be administered as a 20 mg BID dose regimen (10 mg BID less than the adult dose).
 - Dosing for subjects with a weight ≥ 70 kg will be administered as a 30 mg BID dose regimen (same as for adults).
- Dose regimens (dose strength and/or dose frequency) for the remaining subjects in Group 1 will be determined based on PK and safety assessments from the first 8 subjects in Group 1 to complete this period. These data will be reviewed by an independent data monitoring committee (DMC) to determine if it is appropriate to

proceed with dosing the balance of Group 1 subjects and to proceed with dosing in the Group 2 subjects.

- For the remaining subjects in Group 1, the dose strength and/or dose frequency will be adjusted for any safety concerns or for unexpected changes in exposure. In the event of a dose regimen adjustment, some or all of the first 8 subjects in Group 1, depending on weight, will return to the site for the appropriate dosing adjustment. Group 2 will open to enrollment once at least 8 subjects from Group 1 have completed the 2 weeks of apremilast dosing, PK data analysis, and safety assessments and an evaluation of these data by the DMC has been completed.

Group 2 (ages 6 to 11 years, inclusive; weight \geq 15 kg)

- At least 8 subjects will initially be enrolled into Group 2 and will weigh \geq 15 kg. The dose regimens (dose strength and/or dose frequency) for these first 8 subjects will be based upon the PK and safety assessments from the first 8 subjects in Group 1. If PK and safety are not affected by age and body weight, 20 mg BID will be administered to Group 2 children.
- Dose regimens (dose strength and/or dose frequency) for the remaining subjects in Group 2 will be determined based on PK and safety assessments from the data collected from the first 8 subjects in each group. These data will be reviewed by an independent DMC to determine if it is appropriate to proceed with dosing the balance of Group 2 subjects.
- For the remaining subjects in Group 2, the dose (dose strength and/or dose frequency) will be based upon the subject weight as determined by the PK and safety assessments. The dose strength and/or dose frequency will be adjusted for any safety concerns or for unexpected changes in exposure. In the event of a dose regimen adjustment after the second PK and safety assessment, the first 8 subjects in Group 2 will return to the site for the appropriate dosing adjustment.

An independent DMC will review available safety and PK data at the following timepoints:

1. After the first 8 subjects in Group 1 have completed the first 2 weeks of apremilast dosing, PK, and safety assessments.
2. After the first 8 subjects in Group 2 have completed the first 2 weeks of apremilast dosing, PK, and safety assessments.

Treatment administration and schedule are discussed in Section 8.2.

At this time, there are no consistent AEs or laboratory findings that would generally constitute a reliable stopping rule for this study. Subjects will be monitored for AEs, vital signs, and laboratory assessments at each study visit. All AEs, clinically significant changes in laboratory measures and clinically meaningful changes in vital signs will be recorded. Clinically meaningful changes that increase the risk to the subject, as assessed by the Investigator or Sponsor, may result in discontinuation of the subject from the study. Subjects who have psoriasis disease flare at anytime during the treatment (PK, or extension treatment period) of the study and require additional psoriasis medication including conventional systemic therapies such

as methotrexate, systemic corticosteroids, or biologics, will be discontinued from the study and treated according to local treatment guidelines.

The study will be conducted in compliance with International Conference on Harmonisation (ICH) Good Clinical Practices (GCPs).

Figure 1: Overall Study Design

PK= Pharmacokinetics; OL= Open Label (Apremilast); F/U= Follow Up

Figure 2: Subject Treatment Groups

Group 1:

N=16

Ages: 12 to 17 years, inclusive

Weight: ≥ 35 kg

Group 1:

Initial Dose:

20 mg BID for subjects weighing ≥ 35 kg to < 70 kg

30 mg BID for subjects weighing ≥ 70 kg

[figure not shown]

Figure 2: Subject Treatment Groups (Continued)

[figure not shown]
Group 2:

N=16

Ages: 6 to 11 years, inclusive

Weight: ≥ 15 kg

Dose: Based upon completion of PK and safety data analysis from at least 8 subjects from Group 1.

BID = twice daily; N = number of subjects; PK = pharmacokinetic; TBD = to be determined.

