This study will be conducted in subjects aged 6 to 17 years, inclusive, with chronic moderate to severe plaque psoriasis, defined as Psoriasis Area Severity Index (PASI) ≥ 12 , Body Surface Area (BSA) $\geq 10\%$, and static Physician Global Assessment (sPGA) of ≥ 3 (moderate to severe) [See [Appendix A](#)], diagnosed at least 6 months prior to Screening. Subjects whose psoriasis is inadequately controlled by or inappropriate for topical psoriasis therapy will be included.

Previous treatment with one systemic agent will be allowed but subjects treated with more than one systemic agent will be excluded. Subjects must be able to swallow apremilast tablets.

Length of Study

The study will last for up to a total of 107 weeks which includes screening, treatment (PK portion of the study and the extension treatment period), two short-term follow-up periods and a long-term follow-up period.

Each subject will undergo a screening period of up to 5 weeks, an initial treatment period of 2 weeks, and an extension treatment period of 48 weeks, that will allow subjects access to apremilast treatment if medically appropriate (following the completion of the 2 week PK portion). Regardless of when they stop treatment, subjects should complete the post treatment follow-up visits at 4 and at 8 weeks after the last dose. An additional long-term follow-up should be performed 52 weeks after the last dose of apremilast. All subjects should complete the final follow-up visit at Week 102 or at a timepoint 52 weeks after the last dose of apremilast was taken in subjects who have withdrawn at any time prior to Week 50.

The End of Trial is defined as either the date of the last visit of the last subject to complete the post treatment follow-up, or the date of receipt of the last data point from the last subject that is required for primary, secondary and/or exploratory analysis, as prespecified in the protocol, whichever is the later date.

Study Treatments

Apremilast doses of 10-mg, 20-mg or 30-mg tablets have been selected to determine the dose range in adolescents and children with moderate to severe plaque psoriasis. These pediatric dosages are expected to achieve exposures similar to those achieved in adult psoriasis and psoriatic arthritis (PsA) subjects treated with apremilast 30 mg orally twice daily (BID).

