1.3. Human Pharmacology

To date, no studies with apremilast have been conducted in subjects < 18 years of age.

In healthy adult subjects under fasting conditions, apremilast is rapidly absorbed following oral administration. Apremilast demonstrates linear pharmacokinetics, with area under the plasma concentration-time curve (AUC) increasing in a dose-proportional manner through 50 mg BID or 80 mg once daily. Co-administration with food does not affect the PK bioavailability of apremilast (CC-10004-CP-022). Apremilast is primarily eliminated as metabolites formed via both cytochrome P450 (CYP)-mediated oxidative metabolism (and subsequent glucuronidation) and non-CYP-mediated hydrolysis, with less than 3% excreted unchanged in urine (CC-10004-PK-002). Only 2 minor human apremilast metabolites retain pharmacologic activity, indicating that the in vivo pharmacological activity of apremilast is attributed to the parent compound. The plasma clearance of apremilast is on average about 10 L/hr in healthy subjects (CC-10004-CP-012), with a terminal elimination half-life of approximately 6 to 9 hours. CYP3A4, CYP1A2, and CYP2A6 all participate in apremilast metabolism. Co-administration with ketoconazole increased mean apremilast area under the plasma concentration-time curve from time zero to infinity ($AUC_{0-\infty}$) and maximum plasma concentration of the drug (C_{max}) by approximately 36% and 5%, respectively, but did not alter the elimination half-life of apremilast (CC-10004-PK-005). Co-administration of multiple oral doses of rifampin increased apremilast apparent clearance by about 9.6 L/h to 34.5 L/h, which resulted in a decrease in apremilast mean AUC (approximately 72% lower) and C_{max} (approximately 43% lower) relative to that of apremilast given alone (CC-10004-CP-025). Methotrexate (MTX), a commonly prescribed anti-inflammatory drug, does not affect apremilast PK exposure. Apremilast does not affect the PK exposure of MTX and its metabolite, 7-OH MTX (CC-10004-PK-010). Hepatic impairment does not affect apremilast exposure (CC-10004-CP-011), and thus no dose adjustment is necessary for subjects with hepatic impairment. In the subjects with mild renal impairment, there were no clinically meaningful differences in the PK of apremilast relative to the matched healthy group. There were an ~22% higher $AUC_{0-\infty}$ and ~13% lower C_{max} of apremilast noted in the moderate renal impairment group relative to the matched healthy subject group, however, the differences noted were not statistically significant. Moreover, when compared to the healthy subjects matched to the mild renal impairment group, the mean AUC from moderate renal impaired subjects were comparable and the mean C_{max} was 18% lower. Thus, the numerical differences noted in the moderate renal impairment group are likely within the between-subject variability of apremilast exposure and are not clinically meaningful (CC-10004-CP-029). In subjects with severe renal impairment, a single oral dose administration of a 30-mg apremilast tablet resulted in an increase in overall mean exposure ($AUC_{0-\infty}$) by approximately 88% (CC-10004-CP-019). Apremilast PK and exposure are comparable across ethnic groups of Caucasian, Japanese and Chinese subjects (CC-10004-CP-018). Analyses showed apremilast exposure is also similar among Hispanic Caucasians, non-Hispanic Caucasians, and African Americans. Apremilast exposure (AUC) in elderly healthy subjects (70.5 ± 4.15 years of age [mean ± standard deviation (SD)]) was approximately 13% higher than that in young healthy subjects (34.3 ± 7.17 years of age [mean ± SD]; CC-10004-CP-024) although not statistically different. Young and elderly combined, apremilast AUC exposure was approximately 30% higher in females than in males.

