
The metabolic profile of a single 20-mg oral dose of [¹⁴C]-apremilast was characterized in a healthy volunteer absorption/distribution/metabolism/excretion (ADME) study. The mean total urinary and fecal radioactive recovery of apremilast (and its metabolites) was 97.1%, with mean contributions of 57.9% and 39.2% from urine and feces, respectively (CC-10004-PK-002).

Detailed information regarding the available pharmacology, toxicology, drug metabolism, clinical studies, and safety profile of apremilast are available in the Investigator's Brochure.

However, when apremilast is given to subjects whose body weights range from 15 kg to < 70 kg, initial dosing regimens should be adjusted based on body weight. As a result, the proposed dosing regimen in this study will be weight-based and a staggered, stepwise study design (starting enrollment with older and heavier adolescents) will guide dosing of subsequently enrolled subjects (younger and lower body weight children).

The PK and pharmacodynamics (PD) of apremilast in pediatric subjects have not been investigated. Considering the similarity of the disease process between adult and pediatric patients, it is appropriate to choose the dose for the pediatric population that will provide overall drug exposure similar to that of the US Food and Drug Administration (FDA), Health Canada, and the European Medicines Agency (EMA) approved adult dose in psoriasis, assuming a similar exposure and response relationship in adult and pediatric patients.

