4.2. Study Design Rationale

There is a paucity of treatments available for pediatric patients with moderate to severe psoriasis. Consequently, these subjects are treated off-label with the same systemic agents prescribed for adults. The currently available systemic therapies for psoriasis are associated with significant cumulative toxicities and are associated with risks of hepatic, renal and neurological toxicities that often require routine clinical and laboratory monitoring, as well as an increased risk of infections and malignancies. Given the chronic nature of psoriasis, there is a need for medication that can be dosed chronically with less risk. It is, therefore, important for new medications to demonstrate both efficacy and safety with continuous use. Apremilast provides a favorable

benefit/risk profile supporting the use of APR 30 BID in the treatment of adult patients with moderate to severe plaque psoriasis who are candidates for systemic and phototherapy.

Adolescents and children may differ from adults in their ADME of apremilast, hence evaluation of the safety and PK properties of apremilast in adolescents and children prior to initiation of an efficacy study in this subject population is warranted. Although apremilast has only been investigated in adult subjects, it is known that there is a general similarity of disease process, as reflected in PD parameters, between adult and pediatric populations. Assuming a similar exposure-response relationship in adults compared to adolescents and children, it is appropriate to initiate dosing in the pediatric population at a dose of 20 or 30 mg BID, depending on weight, that will provide overall drug exposure similar to that associated with the selected optimal adult dose.

In CC-10004-PSOR-008-PK, the concentration versus time profile of apremilast was well described by a population PK model.

A comparable exposure in pediatric subjects is expected to achieve a similar clinical response seen in psoriasis adult patients following 30 mg BID.

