10.9. Interim Analysis

No formal interim analysis is planned for this study. However, an extract of the PK and 2 weeks of safety data from the initial 8 adolescent subjects enrolled into Group 1 will be used to model the most appropriate dose for subsequently enrolled subjects (such that the exposure will be similar to the exposures in adult subjects administered apremilast 30 mg BID).

Pharmacokinetic data and 2-week safety data from at least 8 Group 1 subjects will be utilized to determine the appropriate dosage (dose strength/dose frequency) for subjects enrolled into Group 2.

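### Read as written, the condition for giving Group 2 children 20 mg BID conflicts with the protocol's target of adult 30 mg BID exposure

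*Protocol*

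**What the plan says.** **The conditional sentence.** For the first Group 2 subjects (6 to 11 years, at least 15 kg), Section 4.1 says: "If PK and safety are not affected by age and body weight, 20 mg BID will be administered to Group 2 children". The Protocol Summary, under Study Treatments, has the same sentence.

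**The target.** It is stated in four places:
- Protocol Summary, Study Treatments: "These pediatric dosages are expected to achieve exposures similar to those achieved in adult psoriasis" and psoriatic arthritis on 30 mg BID.
- Section 1.3: the pediatric dose should give exposure similar to that of the approved adult dose.
- Section 4.2: a starting dose of 20 or 30 mg BID by weight, "that will provide overall drug exposure similar to that associated with the selected optimal adult dose".
- Section 10.9: Group 1 data will be used to model the dose for later subjects, "such that the exposure will be similar to the exposures in adult subjects administered apremilast 30 mg BID".

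**Linearity.** Section 1.3: "Apremilast demonstrates linear pharmacokinetics, with area under the plasma concentration-time curve (AUC) increasing in a dose-proportional manner", up to 50 mg BID, so 20 and 30 mg BID are both covered.

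**Group 1 tiers.** Section 4.1 gives adolescents 20 mg BID from 35 to <70 kg and 30 mg BID from 70 kg.

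**Weight premise.** Section 1.3 says that initial regimens between 15 kg and <70 kg should take account of body weight.

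**The concern.** The sentence ties a dose below the adult dose to a finding that age and weight make no difference. With linear PK, that finding would mean children clear the drug as adults do, and a lower dose would then give lower exposure. The dosing sentence and the modelling aim in Section 10.9 could not both be followed.

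The sentence bears on the first exposure of the youngest and lightest subjects, in a study whose primary objective is to select a pediatric dose. A DMC that applied the sentence literally would be working against the target it is meant to serve.

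**Working it through.** The protocol makes no sample size calculation (Section 10.3) and states no exposure figure to reproduce. The check uses its own dose, linearity and target statements.

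**Formula.** At steady state with linear PK, AUC over a dosing interval = dose / (CL/F), so

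ratio to target = (20/30) × (adult CL/F ÷ child CL/F).

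**Reading 1: age and weight do not affect PK.** Child CL/F equals adult CL/F, and the ratio is 20/30 = 0.67, or 33% below target, at every weight. Using the adult clearance of about 10 L/h in Section 1.3 as CL/F, for illustration only, the interval AUCs are 30/10 = 3 mg·h/L (3000 ng·h/mL) and 20/10 = 2 mg·h/L (2000 ng·h/mL). Clearance cancels from the ratio.

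Conversely, a ratio of 1 at 20 mg BID needs child CL/F = 20/30 = 0.67 of the adult value. That would itself be an effect of age or weight.

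**Reading 2: exposure is similar across the Group 1 tiers.** Equal AUC at 20 and 30 mg BID requires

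CL/F (30 mg tier) ÷ CL/F (20 mg tier) = 30/20 = 1.5.

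Clearance then depends on weight, so the stated condition is false. If CL/F were flat across the tiers instead, AUC would differ 1.5-fold. AUC and CL/F cannot both be flat. This comparison needs both tiers among the first 8 subjects, which the protocol does not require.

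**Direction at 15 to <35 kg.** The protocol gives no weight exponent. Assume CL/F proportional to weight^b and an adult reference of 70 kg (in brackets, 90 kg):

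| b (assumed) | ratio at 15 kg | ratio at 35 kg |
|---|---|---|
| 0 | 0.67 (0.67) | 0.67 (0.67) |
| 0.4 | 1.23 (1.37) | 0.88 (0.97) |
| 0.75 | 2.12 (2.56) | 1.12 (1.35) |
| 1 | 3.11 (4.00) | 1.33 (1.71) |

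The ratio can fall on either side of 1. The table shows only that the direction is not determined. The larger values would arise only if a weight effect went unrecognised, or if the condition meant flat exposure.

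**How much 8 subjects can show.** Assume a log-log regression of clearance on weight, weights evenly spread over 35 to 90 kg, and between-subject CV of 30% to 50%. The 95% half-width for the exponent is then 0.83 to 1.33, and power to detect a true exponent of 0.75 is 46% down to 21%. All 8 subjects are at least 12 years old and at least 35 kg, so anything below 35 kg is extrapolation.

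**The case against.** **The intended meaning may be innocent.** The sentence names no adult comparison. In context, 20 mg BID is the regimen already reduced for subjects below 70 kg. The sponsor may have meant only to carry it forward if Group 1 shows nothing unexpected. This is plausible as intent, but it is not what the sentence says, and it presupposes the weight effect that the condition denies.

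**The sentence does not act alone.** This stands. The sentence before it bases the first Group 2 regimens on Group 1 data. Section 4.1 also says: "Doses for younger and lower body weight subjects will be adjusted based on safety and PK data from older and heavier subjects". Figure 2 fixes no Group 2 dose, Group 2 opens only after DMC evaluation, and a second review can change the regimen of the first 8 children. If a weight effect is recognised, the condition fails and the sentence does not apply.

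**The target is similar, not equal, exposure.** This is fair for small deviations, and the b = 0.4 row shows that a modest weight effect could keep exposure near target. But with adult clearance, a ratio of 0.67 is the exposure of an adult on 20 mg BID. The protocol itself separates the two adult doses: Section 1.4 reports PASI-75 response of 29% at 20 mg BID and 41% at 30 mg BID, and the higher was taken forward.

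**Definitions may sit elsewhere.** A reader might infer that having no criterion for an unaffected PK is a defect in itself. The document does not support that. Section 10.8 plans a covariate analysis, the DMC charter and any analysis plan are not shown, and some exposure rationale may be blacked out. But a definition held elsewhere would not reconcile the sentence as worded with the target.

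**Conclusion.** The conditional sentence and the exposure target conflict as written. On the plain reading, meeting the condition gives 20/30 = 0.67 of target exposure. On the charitable reading, the condition is misstated, because similar exposure across the Group 1 tiers requires a 1.5-fold difference in CL/F. Both figures rest only on the protocol's doses and its linearity statement.

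The reach is limited, mainly to the first 8 Group 2 subjects and to what the first DMC review is asked to judge.

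Two stronger conclusions are tempting and not supported:
- That Group 2 children will be under-exposed or over-exposed. The weight effect is unknown, the ratios depend on assumed exponents and reference weights, and they fall on both sides of 1.
- That the protocol commits all of Group 2 to a single regimen. Section 4.1 bases dosing of the remaining Group 2 subjects on weight, after review of the first 8 in each group.

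**What to change.** - Reconcile the conditional sentence in the Protocol Summary and Section 4.1 with the target in the Protocol Summary and Sections 1.3, 4.2 and 10.9.
- Express the condition as predicted exposure relative to adult 30 mg BID, and name the PK parameter. Section 3.1 lists both AUC over 12 hours and CL/F, and the two cannot both be flat across the Group 1 tiers.
- For the first DMC review, use the population PK model already planned in Section 10.8 to show predicted exposure relative to adult 30 mg BID, with uncertainty, across the Group 2 weight range. Mark 15 to <35 kg as extrapolated.

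The cost is wording in those sections and a small simulation, with no extra subjects, visits or samples. The drawback is that predictions from 8 adolescents will be imprecise, but that imprecision is itself something the DMC should see. Which dose or dosing rule is right is for the sponsor and clinicians to settle, and none is proposed here.
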